6.3.3 Questionnaire 2 (14 days after vaccination)

- questions about any events that are open since questionnaire 1. Treatment, recovery and severity data: earlier entries can be changed.
- questions about any new unsolicited events that have started after completion of questionnaire 1, including any occurrence of fever.
- did your child have changes in medication

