3.2 Study description

Toddlers (14 months old) will receive at vaccination centers NeisVac-C® vaccination with either

- “old” lots produced in Beltsville (group B), or
- “new” lots from Orth/Donau (group A), simultaneously with MMR vaccine.

From 4 full days after the vaccines were administered, parents will receive web-based questionnaires with questions about any ADRs that occurred after vaccination.

The 1st questionnaire is sent at day 5 and covers days 1, 2, 3 and 4.

The 2nd questionnaire will be sent after two weeks and covers days 5 to 14.

The 3rd questionnaire will be sent after four weeks and covers days 15 to 28.

Day numbers are defined as:

- Day 1: day of vaccination, e.g. Monday
- Day 2: 1st day after vaccination, e.g. Tuesday
- Day 3: 2nd day after vaccination , e.g. Wednesday
- Day 4: 3rd day after vaccination, e.g. Thursday = last day of fever counting for primary endpoint.
- Day 5: 4th day after vaccination, e.g. Friday

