5.1 Primary study parameter

Proportions of children with fever (rectally measured body temperature of $\geq 38.0^{\circ}\text{C}$) within 4 days after vaccination with NeisVac-C® and MMR.

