6.3.2 Questionnaire 1 (4 days after vaccination)

Start question: did your child experience an adverse reaction/event: Y/N.

If N: have other medicines been used: click to add

If Y: which adverse events have occurred

- injection site reaction, if yes
 - o where did the reaction occur: one or both sites: specify arm/leg/left/right
 - o further questions per injection site
 - tick symptoms: red, warm, pain, swelling, indurated patch, blue, itch, other: please specify
 - size: largest possible diameter in centimeters (rounded upwards)
 - onset time after injection
 - treated, if yes specify
 - recovery status, if recovered: when
 - size will be categorised by diameter <2 cm: mild, 2-5 cm: moderate, >5 cm: severe
- fever, if yes
 - what was temperature (max value, rectally measured): __, __°C
 - onset time after injection
 - treated, if yes specify
 - recovery status, if recovered: when
 - impact as experienced by parents, graded as: not-mildly-moderately-very
- skin rash
 - please describe ...,
 - onset time after injection
 - treated, if yes specify
 - recovery status, if recovered: when
 - impact as experienced by parents, graded as: not-mildly-moderately-very
- less appetite
 - onset time after injection
 - treated, if yes specify
 - recovery status, if recovered: when
 - impact as experienced by parents, graded as: not-mildly-moderately-very
- sleeping less
 - please describe ...,
 - onset time after injection
 - treated, if yes specify
 - recovery status, if recovered: when
 - impact as experienced by parents, graded as: not-mildly-moderately-very
- sleeping more/somnolence
 - onset time after injection
 - treated, if yes specify
 - recovery status, if recovered: when
 - impact as experienced by parents, graded as: not-mildly-moderately-very
- listlessness
 - onset time after injection
 - treated, if yes specify
 - recovery status, if recovered: when
 - impact as experienced by parents, graded as: not-mildly-moderately-very

- vomiting
 - onset time after injection
 - how often
 - treated, if yes specify
 - recovery status, if recovered: when
 - impact as experienced by parents, graded as: not-mildly-moderately-very
- diarrhea
 - onset time after injection
 - how often
 - treated, if yes specify
 - recovery status, if recovered: when
 - impact as experienced by parents, graded as: not-mildly-moderately-very
- (febrile) seizures
 - please describe:
 - what was temperature at the time of the seizure:
 - onset time after injection

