 - treated, if yes specify
 - recovery status, if recovered: when
 - impact as experienced by parents, graded as: not-mildly-moderately-very
- other reactions (more than 1 additional unsolicited reaction can be added).
 - please describe:
 - onset time after injection
 - treated, if yes specify
 - recovery status, if recovered: when
 - impact as experienced by parents, graded as: not-mildly-moderately-very

For all events together it will be asked :

- was the child seen by a doctor for this complaint.
- did any of the reported events lead to one of the following:
 - o No, if Yes, tick if applicable:
 - hospitalisation
 - immediately life threatening
 - death

Any other data to label the reported AE as serious according to CIOMS criteria will be obtained from free text entries. They will be individually assessed by the Lareb investigator, and further regarded as SAE if applicable.

Co-medication:

- did your child have changes in medication.
Medication listed at Start are shown again and open for editing (start date, stop date, dose, add new)

Characteristics of the household

- how many children are living in your household (including the vaccinee):
choose from list: 1, 2, 3, 4, 5, 6 or more.
- does your child go to guest parents, daycare centre, kindergarten

Any reported complaints that are not resolved will be open to edit in next questionnaires.

In addition, parents are asked to report new events if applicable. All new events are to be entered in a free text field, and will be manually coded.

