6.4 Reminders

Parents are sent reminders if the filled questionnaire is not received by Lareb.

- after Q1 (day 5), reminder at day 7, valid time of return: day 8
- after Q2 (day 14), reminder at day 16, valid time of return: day 18
- after Q3 (day 28), reminder at day 32, valid time of return: day 36.

Questionnaires received after the valid time of return will not be included in the Per Protocol analysis.

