9.1 Statistical formulation of the study hypothesis

The primary endpoint in this study is defined as the number of children with fever reactions within 4 days after vaccination with NeisVac-C®. Fever defined as rectally measured 38° Celsius or higher.

Kroesbergen et al found in a study following 863 Dutch children that fever occurred in 46 (5,3%; 95% CI 3,83-8,83) of children at day 0, 1 and/or 2. Fever at days 3 and 4 is not mentioned. A graph shows that the daily prevalence of fever is about max 3,5%. From day 5 the % of children with fever is rising to 19% at day 9 (ascribed to simultaneously given MMR vaccine).

Our primary endpoint is based on pooled daily presence of fever from days 0 to 4 after vaccination. Based on Kroesbergen et al we expect this to occur in about 6% of the children (95% CI 4,44-7,71, when 52/863 cases).

Baby clinics will be randomized to vaccinate with either product

- investigational new product Orth/Donau (Austria) = Active = Group A
- comparator old product Beltsville (US) = Reference = Group B

Randomisation procedure: to be described

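### The Questionnaire 1 fever item records one undated, later-editable maximum temperature, so a few fevers reached after day 4 could count in the day 1–4 primary endpoint

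*Protocol*

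**What the plan says.** **Endpoint and window.** Protocol 5.1 defines the primary parameter as "Proportions of children with fever (rectally measured body temperature of" at least 38.0 °C, within 4 days of vaccination. Section 3.2 numbers the vaccination day as day 1 and calls day 4 the "last day of fever counting for primary endpoint". Section 1.1 explains the window: MMR side effects have a latency of about 5 days, so earlier fever is more likely due to NeisVac-C.

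**The form.** Section 3.2 says: "The 1st questionnaire is sent at day 5 and covers days 1, 2, 3 and 4". In 6.3.2 the fever item asks "what was temperature (max value, rectally measured"), then onset time, treatment, recovery and the impact felt by the parents. No day is asked for the maximum. Under 6.5 parents measure when they suspect fever. The form sets no lower limit, so an entry below 38.0 °C is possible.

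**Late return and editing.** Section 6.4 gives: "after Q1 (day 5), reminder at day 7, valid time of return: day 8". Section 6.3.2 adds: "Any reported complaints that are not resolved will be open to edit in next questionnaires". Section 6.3.3 reopens events still open since Questionnaire 1 and states: "Treatment, recovery and severity data: earlier entries can be changed". It sends fever that began after Questionnaire 1 was completed to a new entry. Section 6.3.4 asks about open events but does not repeat the sentence on changing entries.

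**Safeguard.** Section 12.3 says that changes are logged. Nothing in the protocol ties the primary endpoint to the temperature as first submitted, or to a maximum reached on days 1–4.

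**The concern.** The four-day window is the design's means of separating NeisVac-C fever from MMR fever. It works only if the temperature that decides case status was measured inside the window. The form dates the start of the fever, not its maximum.

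Take a child with 37.8 °C from day 4, unresolved when Questionnaire 1 is completed, who reaches 39.2 °C in the MMR fever phase. If the parent updates the open entry, the record shows onset on day 4 and a maximum of 39.2 °C, which looks like a primary-endpoint case. A form returned on days 6–8 could show the same thing with no edit.

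Every child receives MMR, so such cases should be added about equally to both groups. Equal additions pull a risk ratio above 1 towards 1. In a non-inferiority comparison that works in favour of the claim.

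**Working it through.** **1. Which records can change status.** A false case by editing needs all of the following:
- fever ticked in Questionnaire 1 with onset on days 1–4;
- a maximum below 38.0 °C, or blank;
- the event still open when the form was completed;
- the parent treating the later rise as the same event and replacing the value.

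An entry already at or above 38.0 °C counts whatever is edited. A fever starting after Questionnaire 1 is a separate entry.

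**2. Day scales.** Section 9.1 reports an earlier Dutch study of 863 children: "From day 5 the % of children with fever is rising to 19% at day 9". That section counts from day 0, whereas 3.2 counts from day 1. On that reading the rise starts on study day 6 and the 19% falls on study day 10. Questionnaire 1 goes out before the rise, but returns on days 6–8 overlap its start.

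**3. Inputs for the size.** Section 9.2 gives 6% fever in group B, 9% in group A at the margin (RR 0.09/0.06 = 1.5), one-sided alpha 0.025 and n = 1215 per group. The sample size is only a base here and is not disputed by this point. The two-proportion formula for 6% against 9%, (0.06×0.94 + 0.09×0.91)×(1.960 + 0.842)²/0.03², gives 1207, close to 1215.

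**4. Formulas.** Let e be the share of all children wrongly added as cases, equal in both groups, with children taken as independent:
- pA = 0.09 + e; pB = 0.06 + e; RR = pA/pB
- SE(log RR) = √[(1 − pA)/(1215 pA) + (1 − pB)/(1215 pB)]
- P(upper 95% limit < 1.5) = Φ[(ln 1.5 − ln RR)/SE − 1.96]

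Check at e = 0: SE = √(0.91/109.35 + 0.94/72.9) = 0.146, RR = 1.500, and the probability is Φ(−1.96) = 2.5%, as it should be.

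**5. Results at a true RR of 1.5.**

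| e (points) | False cases per group | Observed RR | False claim |
|---|---|---|---|
| 0 | 0 | 1.500 | 2.5% |
| 0.1 | 1.2 | 1.492 | 2.7% |
| 0.5 | 6.1 | 1.462 | 3.8% |
| 1.0 | 12.2 | 1.429 | 5.5% |

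At a true RR of 1, (0.06 + e)/(0.06 + e) = 1.00 for every e.

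**6. A plausible range for e.** The documents give no rates, so these are assumptions:
- 1%, 2% or 3% of children have a fever entry below 38.0 °C;
- 10%, 30% or 50% of those are still open;
- 19%, 50% or 100% of those are later raised to 38.0 °C or more.

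The product runs from 0.01×0.10×0.19 = 0.02% to 0.03×0.50×1.00 = 1.5%, or 0.2 to 18.2 children per group. Of the 27 combinations, 22 lie at or below 0.5%. The extreme of 1.5% gives RR 1.400 and a false-claim rate of 7.6%, and needs every assumption at its upper end.

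**The case against.** **Temperature is not named as editable.** Section 6.3.3 lists treatment, recovery and severity. For fever, severity could mean the impact graded by parents. This stands: that temperature can be overwritten is an inference. It is supported by the unrestricted sentence on unresolved complaints in 6.3.2, and by the fact that temperature is the only measured severity item for fever.

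**The documents limit the path.** Questionnaire 1 is stated to cover days 1–4, and new fever goes to a new entry. Onset and recovery are recorded. A blank temperature might also be excluded under 9.3 as a major deficiency. All this narrows the path. It does not close it for a raised temperature already open at Questionnaire 1, because onset alone cannot date the maximum.

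**The first value is recoverable.** Changes are logged (12.3) and filled questionnaires are transferred weekly (10.2.2). Which logged value feeds the endpoint is a derivation rule that may stand in an analysis plan not shown here. This stands for edited values. It does not help with the day of the maximum: no analysis plan can recover what the form never asked.

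**Stronger readings that the documents do not support.**
- A reader might infer that MMR fever generally flows back into the primary numerator. Only open entries that are below 38.0 °C or blank can change status.
- A reader might infer that Questionnaire 3 carries the same permission on severity data. That sentence is in 6.3.3 only.
- A reader might assume 2 points of contamination, which gives RR 1.375 and a 10.1% false-claim rate. That means 0.02×1215 = 24.3 false cases per group beside 0.06×1215 = 72.9 expected, and it lies beyond the range in the working.

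**Conclusion.** The point holds in a limited form. The fever item as written cannot show that the deciding temperature was reached on days 1–4. Late return and later editing leave a narrow way for a post-day-4 maximum to count.

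The likely effect is small. With 0.1 to 0.5 points added equally to both groups, a true risk ratio of 1.5 is seen as 1.49 to 1.46 and the false non-inferiority rate goes from 2.5% to 2.7%–3.8% (5.5% at 1 point). The risk ratio is not biased if it is truly 1. These sizes rest on an assumed contamination rate, equal addition in both groups, independent children and a normal approximation.

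This is no ground for doubting the design as a whole. It is worth correcting because the bias favours the claim, the missing day cannot be reliably recovered afterwards, and the remedy costs almost nothing.

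**What to change.** - **6.3.2:** ask for the highest temperature on days 1–4 and the day on which it was measured.
- **6.3.3 and 6.3.4:** put any later, higher temperature of an open fever in a new dated field, and do not overwrite the Questionnaire 1 value. Recovery and treatment can stay editable.
- **5.1 and 9.6:** state that the primary endpoint uses the Questionnaire 1 temperature as first submitted, with its day in days 1–4. Take genuine typing corrections from the change log described in 12.3.

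If forms are already in use, the first-submitted value can still be taken from that log, but the day of the maximum cannot.

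Cost: the extra date entries on the forms, a sentence in the endpoint definition, and manual handling of parents' typing corrections. No extra children or visits are needed.

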STUDY TITLE	A non-interventional, open observational non-inferiority study in two cluster- assigned cohorts of children aged 14 months into the safety of NeisVac-C® vaccines manufactured at two different production sites and given simultaneously with measles-mumps-rubella vaccine, assessed by web-based intensive monitoring
STUDY NAME	Peuterprik
STUDY PRODUCT(S)	NeisVac-C®, Meningococcal Group C Polysaccharide Conjugate Vaccine Adsorbed, 'old' and 'new'
STUDY PHASE	Post marketing surveillance
STUDY OBJECTIVES	To compare the safety of the NeisVac-C® bulk material produced at Baxter in Orth/Donau (new) (group A) with the material produced in Beltsville (old) (group B) in toddlers aged 14 months, administered simultaneously with MMR vaccine.
Primary	The primary endpoint is the proportions of subjects with fever reactions within 4 days after administration.
Secondary	The secondary endpoints are proportions of subjects with 
 - solicited other systemic and local reactions within 4 days after administration - non-solicited other systemic and local reactions within 4 days after administration - non-solicited other systemic and local reactions from 5 to 28 days after administration
STUDY DESIGN	non-interventional, open observational non-inferiority study with two cluster- assigned cohorts
SUBJECTS	At least 2430 healthy toddlers aged 13-18 months old, eligible to receive MenC and MMR vaccinations according to the NIP
INCLUSION CRITERIA	
 - age 13-18 months old (boundaries included) - eligible to receive MenC and MMR vaccinations according to the NIP
EXCLUSION CRITERIA	
 - children receiving either MenC or MMR vaccine and not both at same time - children with parents that are not able or willing to understand or fill the questionnaires
STUDY PARAMETERS	Primary: reactogenicity defined as % of children with rectal temperature 38,0 Celsius and above during the first 4 days after vaccination Secondary: other solicited and unsolicited complaints and symptoms at injection site as well as systemic reactogenicity
STUDY GROUPS	Two study groups of similar size will be formed according to the MenC vaccination that has been given at the baby clinics, i.e. NeisVac-C® from either Orth/Donau (group A) of Beltsville (group B).
STUDY PRODUCT REGIME	Children receive one injection of either MenC vaccine while MMR vaccine is given at a different injection site simultaneously

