2.2 Secondary study objective(s)

Secondary objective of this study is to investigate

- the safety profile with other parameters (solicited and non-solicited) within 4 days after simultaneous injections of either MenC, and MMR vaccines.
- the safety profile of these vaccines with non-solicited parameters from 5 to 28 days after injection.

CHAPTER 3. STUDY DESIGN

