5.2 Secondary study parameter(s)

Proportions of children with solicited other systemic and local reactions within 4 days after vaccination with NeisVac-C® and MMR.

The occurrence of the following reactions will be asked actively:

Local (injection site) reactions at the NeisVac-C® and/or MMR injection site

- redness, warmth, pain, swelling, induration, blue, itch

General (systemic) reactions

- rash
- decreased appetite
- less sleeping
- listlessness
- sleepiness/somnolence
- vomiting
- diarrhea
- (febrile) seizures

In addition a free text field is available so that symptoms not listed above can be reported.

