6.3.4 Questionnaire 3 (28 days after vaccination)

- questions about any events that are open since questionnaires 1 or 2
- questions about any new unsolicited events that have started after completion of questionnaire 2, including any occurrence of fever.
- did your child have changes in medication
- is your child healthy at present
- do you have any other remarks (contact form to be sent to email server; not part of the data collection of the study)
- thank you!

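### Fever on days 5-28 has no consistent endpoint status, and no temperature field is described for it

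*Protocol*

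**What the plan says.** The synopsis makes fever within 4 days the primary endpoint. It then lists as the late secondary endpoint the proportion of subjects with "non-solicited other systemic and local reactions from 5 to 28 days after administration". Section 2.2 words the same objective as "the safety profile of these vaccines with non-solicited parameters from 5 to 28 days after injection". Section 5.2, where the secondary parameters are set out, has "Proportions of children with solicited other systemic and local reactions within 4 days after vaccination with NeisVac-C® and MMR" and nothing for days 5-28.

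On data collection, the fever item of Questionnaire 1 (section 6.3.2) asks "what was temperature (max value, rectally measured") with a field in °C, then onset time, treatment, recovery and impact. For new events in the later questionnaires, the end of that section says: "All new events are to be entered in a free text field, and will be manually coded". Section 6.3.3 describes Questionnaire 2 as containing "questions about any new unsolicited events that have started after completion of questionnaire 1, including any occurrence of fever", and section 6.3.4 describes Questionnaire 3 as containing "questions about any new unsolicited events that have started after completion of questionnaire 2, including any occurrence of fever".

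The 38.0°C rectal definition appears in the synopsis and in sections 2.1, 5.1 and 9.1, each time for the 4-day primary endpoint. Section 9.1 also reports from the cited Dutch study: "From day 5 the % of children with fever is rising to 19% at day 9". It ascribes this rise to the simultaneous MMR vaccine.

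**The concern.** Two questions about late fever should have one answer each in the protocol: does a child with fever on days 5-28 count in a secondary endpoint, and what makes it a fever? On the first, the synopsis, section 2.2, section 5.2 and the questionnaires point in different directions, so two analysts could count different children. On the second, the early window records a maximum temperature, while the later forms are described only as free text.

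At stake is the description of an event that the protocol itself expects to be frequent after day 5. If temperatures are not collected, fever on days 5-28 cannot be reported on the same definition as fever on days 1-4, and no analysis plan can put this right afterwards.

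**Working it through.** The plan gives no figure for this endpoint to reproduce, so the check is mainly a comparison of passages.

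**Step 1: status of late fever.**

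| Place | Window | What it implies for late fever |
|---|---|---|
| Synopsis, secondary endpoints | days 5-28 | Non-solicited *other* reactions. Beside a fever primary endpoint, *other* may mean other than fever |
| Section 2.2 | days 5-28 | Non-solicited parameters, without *other*. Fever not excluded |
| Section 5.2 | days 1-4 only | No late parameter listed |
| Sections 6.3.3 and 6.3.4 | after Questionnaires 1 and 2 | Fever asked for by name, but classed as unsolicited |

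An event that every parent is asked about by name is solicited in the ordinary sense. Section 5.2 itself introduces its list as reactions asked about actively. The label in 6.3.3 and 6.3.4 is therefore at odds with the protocol's own usage.

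**Step 2: measurement.**

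- Questionnaire 1 fever item: maximum rectal temperature, onset, treatment, recovery, impact.
- Questionnaire 1 item for other reactions, the only free-text event item described in detail: description, onset, treatment, recovery, impact. It has no temperature.
- Questionnaires 2 and 3: new events in free text, with no fields listed for a new fever.

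If the later forms reuse the free-text item, onset would be captured but temperature would not, unless the parent happened to write it down. If they do not reuse it, onset is uncertain too. Onset matters here. Section 3.2 has Questionnaire 2 cover days 5-14, but 6.3.3 asks about events starting after Questionnaire 1 was completed, and section 6.4 accepts that form until day 8. A recorded onset is what places a fever in its window.

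**Step 3: how many children.** Inputs: 1215 per group (section 9.2), 19% at day 9 and 6% expected for the primary endpoint (section 9.1).

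- Late fever at day 9: 0.19 × 1215 = 230.85, about 231 children per group.
- Primary endpoint, whole window: 0.06 × 1215 = 72.9, about 73 children per group.

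The 19% reads as a single-day value, so the proportion with any fever over days 5-28 in that study would be at least as high. The cited study counts from day 0 and section 3.2 from day 1; under either count the peak falls in the Questionnaire 2 window.

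**The case against.** The strongest reply is that nothing important is lost. The word *other* can be read as other than the primary endpoint, which is fever within 4 days, so late fever need not be excluded. Section 2.2 and both later questionnaires fit late fever being reported as a non-solicited event. Section 9.1 defines fever as 38°C or higher, and section 6.5 asks parents to measure rectally whenever they suspect fever, with no limit to the first days. Section 12.3 provides for MedDRA coding, so fever can be tabulated as its own term. Sections 6.3.3 and 6.3.4 are short summaries of the forms and may not list every field.

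Much of this stands. A reader might infer that the late endpoint must either lose its commonest event or be swamped by MMR fever that dilutes any difference between the vaccines. The documents do not support that. Dilution needs a single any-event composite, which the protocol does not specify, and its size would rest on invented rates. The protocol gives no late rate for any event but fever, so it does not show fever to be the commonest. A reader might also infer that the fever threshold changes after day 4. No different threshold is stated; the definition is simply not carried over.

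The reply does not remove the mismatch between the synopsis, 2.2, 5.2 and the questionnaires, or the unsolicited label on a prompted event. A MedDRA term can mark an entry as fever but cannot supply a temperature. Asking parents to measure does not ensure that the value is recorded.

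**Conclusion.** The point holds in a limited form: the status of fever on days 5-28 is inconsistent across the protocol, and no means of applying the 38.0°C definition to it is described. It concerns an event cited at 19% on one day, about 231 children per group if this population behaves like the cited one and 1215 per group are evaluable. Section 9.1 does not say which temperature threshold that 19% rests on.

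The consequence is small. Section 9.4 makes the secondary endpoints descriptive only. Section 9.6 has them analysed similarly to the primary, so relative risks may appear, but without any non-inferiority claim. The primary endpoint, the sample size and the non-inferiority conclusion are untouched, and both groups receive the MMR vaccine to which the late fever is ascribed. No loss of power or bias in the vaccine comparison is shown. This is a cheap improvement, worth making because the missing value cannot be recovered later.

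**What to change.** - In Questionnaires 2 and 3, use the Questionnaire 1 fever item (maximum rectal temperature and onset) in place of a free-text fever entry.
- Class late fever as solicited in sections 6.3.3 and 6.3.4.
- In the synopsis and in sections 2.2 and 5.2, state in matching words two descriptive secondary endpoints for days 5-28: fever of at least 38.0°C with onset in that window, and non-solicited reactions other than fever. Report them on separate rows.

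The cost is the reuse of an existing web item, a few wording changes, one extra table row, and a slightly longer form for parents who report fever. It has to be done before the forms go live.

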6.2 Procedures

Vaccinations take place at the baby clinic / health center of the toddler. Prior to vaccination, the child health physician or nurse reviews the health status of the child to exclude any contra-indication for MenC and MMR vaccinations according to the guidelines of the National Immunisation Programme. These vaccinations are given to all eligible children, regardless of later (non)participation.

Health personnel at the baby clinic will record the vaccinations (name clinic, name and batch no of vaccine, date of vaccination) in the child health dossier, as well as on the vaccination cards, which are sent to the RIVM vaccination registry (DVP), as prescribed in the NIP.

After vaccination, parents are reminded to the letter that they received earlier, and that they still may sign-up for the study with the use of a reporting code. If they intend to participate, baby clinic staff will record the vaccines given at that day, specifically batch numbers, and injection sites. The letter also contains a diary table, to be used by the parents as an aide-memoire, to record any health event that is to be filled in the electronic questionnaires.

Parents of children who have registered to participate will receive a web-based questionnaire at day 5 after the vaccines were administered with questions about any ADRs that occurred within 4 days of vaccination. A second questionnaire will be sent after two weeks, and a third after 4 weeks.

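### Two conflicting definitions of the questionnaire windows can leave events starting on days 5-8 and 15-18 unasked for parents who return Questionnaires 1 and 2 late

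*Protocol*

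**What the plan says.** The protocol defines the period covered by each questionnaire in two ways.

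**Fixed calendar windows.** Section 3.2, where Day 1 is the day of vaccination, states:
- Questionnaire 1 (Q1): "The 1st questionnaire is sent at day 5 and covers days 1, 2, 3 and 4".
- Questionnaire 2 (Q2): "The 2nd questionnaire will be sent after two weeks and covers days 5 to 14".
- Questionnaire 3 (Q3): "The 3rd questionnaire will be sent after four weeks and covers days 15 to 28".

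Section 6.2 repeats the limit on Q1, describing a form "with questions about any ADRs that occurred within 4 days of vaccination".

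**Windows that start at completion of the previous form.** Section 6.3.3 gives Q2 "questions about any new unsolicited events that have started after completion of questionnaire 1, including any occurrence of fever". Section 6.3.4 gives Q3 "questions about any new unsolicited events that have started after completion of questionnaire 2, including any occurrence of fever". Both forms also follow up events still open from earlier forms. The end of section 6.3.2 restricts that carry-forward to complaints that were reported and have not resolved.

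**Return deadlines.** Section 6.4 has: "after Q1 (day 5), reminder at day 7, valid time of return: day 8". For Q2 it sets a reminder at day 16 and a last valid return at day 18.

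**How Q1 opens.** Section 6.3.2 has: "Start question: did your child experience an adverse reaction/event: Y/N". That question carries no dates. Each listed event then has an item for onset time.

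**The concern.** The two definitions agree only if Q1 is completed at once on day 5 and Q2 by the end of day 14. The protocol does not expect this of everyone: it plans reminders and treats returns up to days 8 and 18 as valid.

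Take a child whose fever starts on day 6 and whose parent returns Q1 on day 8. The event lies outside Q1's window in sections 3.2 and 6.2. It also began before Q1 was completed, so Q2's new-event question does not ask for it. The follow-up of open events does not recover it, because it was never reported. The same can happen from day 15 between Q2 and Q3.

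At stake is the secondary objective in section 2.2 on unsolicited events from day 5 to day 28. Its absolute frequencies could be under-counted by an amount that depends on how fast the parent replies. The first gap lies near the start of the MMR fever rise described in section 9.1. No later analysis can recover an event that no form asked about.

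**Working it through.** **Inputs**
- Windows: Q1 days 1-4, Q2 days 5-14, Q3 days 15-28 (section 3.2).
- New-event questions of Q2 and Q3 start at completion of the previous form (sections 6.3.3 and 6.3.4).
- Valid return of Q1: days 5 to 8. Valid return of Q2: days 14 to 18 (section 6.4).
- Length of the secondary window: days 5-28, so 28 − 5 + 1 = 24 days. Of these, days 5-14 are 10 days and days 15-28 are 14 days.

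The protocol gives no figure for coverage, so there is none to reproduce.

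**Step 1: the rules combined.** Let r1 be the day on which Q1 is returned and r2 the day on which Q2 is returned.
- First gap: r1 − 5 full days, or at most r1 − 4 days if the whole return day is counted.
- Second gap: max(0, r2 − 15) full days, or at most max(0, r2 − 14).

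| Q1 returned on day | Full days unasked | Upper limit with part-day | Upper limit as share of days 5-14 |
|---|---|---|---|
| 5 | 0 | 1 | 10% |
| 6 | 1 | 2 | 20% |
| 7 | 2 | 3 | 30% |
| 8 | 3 | 4 | 40% |

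| Q2 returned on day | Full days unasked | Upper limit with part-day | Upper limit as share of days 15-28 |
|---|---|---|---|
| 14 | 0 | 0 | 0% |
| 15 | 0 | 1 | 7% |
| 16 | 1 | 2 | 14% |
| 17 | 2 | 3 | 21% |
| 18 | 3 | 4 | 29% |

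Latest valid return on both forms: 3 + 3 = 6 full days, 6/24 = 25%. Counting part-days: 4 + 4 = 8 days, 8/24 = 33%. Return on days 5 and 14: no full day, and at most part of day 5.

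**Step 2: each definition alone.**
- Section 3.2 alone is contiguous: 0 days uncovered for any return day.
- Section 6.3 alone is also contiguous. Q1's opening question is undated, and each later form starts where the previous one was completed: 0 days uncovered.

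The gap therefore comes from combining the two.

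**Step 3: what changes if a late responder uses Q1's undated question.** A day-6 event entered in a Q1 returned on day 8 is captured, and it is prompted by Q1's checklist. The same event in a child whose Q1 came back on day 5 can be reported only as a new event in free text on Q2 (end of section 6.3.2). There is no gap, but the method of ascertainment for days 5-8 then differs with response speed.

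**Step 4: position of the MMR fever rise.** Section 9.1 reports from the cited Dutch study a rise from day 5 to 19% at day 9. That section counts from day 0. If day 0 is the day of vaccination, these are days 6 and 10 in the numbering of section 3.2. The first gap (days 5-8) thus meets the start of the rise but not the 19% figure. Section 9.1 reports no rise on days 15-18.

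**The case against.** The strongest reply is that the gap appears only when two descriptions are spliced, and that each is complete by itself. Section 6.3 specifies the form content, Q1's opening question there has no date limit, and onset time is collected. The actual screen text is not shown and may carry dates. This stands as far as it goes: the documents show a contradiction that can produce a gap, not a gap that must occur. It does not remove the point, because reading Q1 as open-ended contradicts sections 3.2 and 6.2 and leaves ascertainment dependent on response speed.

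Four stronger inferences are tempting, and the documents do not support them:
- *A quarter of the events of days 5-28 will be missed.* The 25% is a share of days for a parent who is last on both forms. The protocol gives no distribution of return dates, and section 9.1 describes the share of children with fever by day rather than onsets, so the number of lost events cannot be calculated.
- *MMR fever will contaminate the primary endpoint.* Section 3.2 makes Day 4 the last day on which fever counts, and Q1 records onset time. A fever that starts on days 5-8 and is entered on Q1 can be set aside by its onset. For any one event, loss and misplacement on Q1 are also alternatives, not harms that add up.
- *Both gaps fall on the MMR fever rise.* Only the first does, and only at its beginning.
- *The comparison of old and new vaccine is biased.* Clinics are randomly assigned (section 8.2) and parents are not told the product (section 8.1). The protocol gives no reason to expect return timing to differ by group.

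It is also fair to say that the affected endpoint is descriptive and carries no non-inferiority claim (sections 9.4 and 9.6).

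**Conclusion.** The point holds as an internal contradiction with a bounded consequence. Sections 3.2 and 6.2 define one set of windows and sections 6.3.3 and 6.3.4 another. With the return deadlines of section 6.4, the combination can leave part of days 5-8 and 15-18 outside every form's stated window. The ceiling per child is 6 full days, or 8 with part-days, out of 24. For a prompt responder it is no full day.

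This size assumes that parents keep to Q1's four-day limit and read the new-event questions of Q2 and Q3 literally. If they use Q1's undated question instead, nothing is lost, but events on days 5-8 are prompted by a checklist in late responders and left to free text in early ones. Either way, absolute frequencies for the days 5-28 secondary endpoint depend on response speed. The primary endpoint is unaffected. A biased group contrast would require return timing to differ by group.

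The correction is worth making because it costs almost nothing and the lost information could not be restored at analysis.

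**What to change.** Use one window definition in sections 3.2, 6.2 and 6.3.2 to 6.3.4, and show pre-filled calendar dates on each web form:
- Q1: events with onset from the Day 1 date to the Day 4 date.
- Q2: events with onset on or after the Day 5 date, also if they began before Q1 was completed.
- Q3: events with onset on or after the Day 15 date, also if they began before Q2 was completed.

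State that events are assigned to windows by reported onset date, whichever form they were entered on, and that duplicates across forms are removed. Keep the follow-up of open events as it is.

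The cost is rewording the web forms and reconciling a few events reported twice. Sample size, schedule and return deadlines do not change.
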